11.2 Recording of Suspected Adverse Reactions (SARs) and Adverse Device Effects (ADEs)

All observed or volunteered adverse effects (serious or non-serious) and abnormal test findings, regardless of treatment group, if applicable, or suspected causal relationship to the investigational products or, if applicable, other study treatment or diagnostic product(s) will be recorded in the subjects' case histories. For all adverse effects, sufficient information will be pursued and/or obtained so as to permit 1) an adequate determination of the outcome of the effect (i.e., whether the effect should be classified as a serious adverse effect) and; 2) an assessment of the causal relationship between the adverse effect and the investigational products or, if applicable, the other study treatment or diagnostic product(s).

Adverse effects or abnormal test findings felt to be associated with the investigational device or, if applicable, other study treatment or diagnostic product(s) will be followed until the effect (or its sequelae) or the abnormal test finding resolves or stabilizes at a level acceptable to the sponsor-investigator.

11.3 Reporting of Suspected Adverse Reactions, Adverse Device Effects and Unanticipated Problems

11.3.1 Investigator Reporting: *Notifying the study sponsor*

N/A

11.3.2 Investigator Reporting: *Notifying the IRB*

ALL unanticipated events that meet the definition of an Unanticipated Problem will be reported within 1 week of becoming aware of the event. Expected or unrelated adverse effects and potential protocol violations will be recorded and reported in the annual IRB renewal submission. Additionally, the sponsor-investigator will submit a summary of all unanticipated problems that occurred since the beginning of the study at the time of continuing review. Unanticipated events that are not considered serious adverse events, will be reported at the time of continuing review. Copies of each report and documentation of IRB notification and receipt will be kept in the Regulatory Binder.

11.3.3 Investigator Reporting: *Notifying the FDA*

The Sponsor-Investigator (S-I), as holder of the IND, will be responsible for all communication with the FDA and will report to the FDA, any adverse event that is serious, unexpected and for which there is reasonable possibility that the drug caused the adverse event. These must be reported to the FDA as soon as possible, but no later than 15 calendar days after the S-I determines that the information qualifies for reporting. Any fatal or life-threatening SARs will be reported to the FDA as soon as possible, but no later than 7 calendar days after the S-I determines that the information qualifies for such reporting.

The Columbia University Irving Medical Center Sponsor-Investigator must report to the FDA and any affiliate site investigators as follows:

- Any unexpected fatal or life-threatening event must be reported as soon as possible, but no later than 7 calendar days after the sponsor-investigator's initial receipt of the information
- Any findings from epidemiological studies, pooled analysis of multiple studies, or clinical studies, whether or not conducted under an IND, and whether or not conducted by the sponsor-investigator, that suggest a significant risk in humans exposed to the drug must be reported as soon as possible but no later than 15 calendar days after the sponsor-investigator determines that the information qualifies for reporting
- Any findings from animal or in vitro testing whether or not conducted under an IND, and whether or not conducted by the sponsor-investigator, that suggest a significant risk in humans exposed to the drug must be reported as soon as possible but no later than 15 calendar days after the sponsor-investigator determines that the information qualifies for reporting
- Any clinically important increase in the rate of a serious suspected adverse reactions over that listed in the protocol or Investigator Brochure
- Expected SAEs and AEs will be included in the IND Annual Reports

The Sponsor-Investigator will report any UADE that meet the reporting criteria to the FDA within 10 days of the investigator/team becoming aware of the event.

Reportable Adverse events may be submitted on FDA Form 3500A, a Serious Adverse Event Reporting Form, or in a narrative format.

Updates and follow up reports will be submitted as soon as the updated information becomes available to the investigator and/or research team.

11.3.4 DSMC Reporting by sponsor-investigator

Serious adverse events not constituting unanticipated problems are to be reported to the HICCC DSMC. Reporting should occur within 24 hours of knowledge of the SAE occurring at our institution or affiliate sites.

11.3.5 Reporting to Drug Manufacturer by sponsor-investigator

The Sponsor-Investigator will report any serious adverse events that meet the reporting criteria to the Institutional Review Board and DSMC as described above. Since drug stock is being purchased directly from commercial entities, there is no need for adverse event reporting directly to the drug manufacturer.

11.3.6 Reporting Process

Reportable adverse events may be submitted on FDA Form 3500A, the HICCC DSMC Serious Adverse Event Reporting Form, or in a narrative format.

12. DOSE MODIFICATION AND WITHDRAWAL CRITERIA

12.1 Dose modification

Doses of the drug (Panobinostat) will not be reduced. Instead, if the patient recovers from any previous adverse event (AE) or Serious Adverse Event (SAE) and the principal investigator determines that it is in the patient's best interest to proceed with the study therapy for maximal therapeutic benefit, the next scheduled FUS/treatment should be administered. During any cycle, if grade 2 or higher toxicity is unresolved before the next scheduled FUS treatment, treatment will be halted and will be re-evaluated upon resolution of toxicity. The treatment may be resumed for the subject if the toxicity is resolving before the subsequent scheduled FUS treatment.

If the treatment related toxicity experienced toxicity (Grade 2 or higher) persists for more than 21 days or there is ≥ 1 Dose Limiting Toxicity (DLT), the subject will not have the subsequent FUS. If two DLTs occur at the same NOTS level, further enrollment will be halted.

Additional modifications to timing of doses may be performed at the discretion of the PI.

General guidelines: Patients with minor signs of increased intracranial pressure may be managed by steroids and mannitol. If patients develop significant new neurologic deficits or a change in level of consciousness (Grade 2 or higher symptomatic intracranial hemorrhage or stroke), the treatment will be stopped.

Criteria to proceed to subsequent FUS/treatment include :

- Absence of intercurrent active infection or intercurrent illness
- Resolving treatment related toxicity experienced in prior FUS /treatment to grade 2 or less
- Patient decides to withdraw

Within each cycle, if 1 DLT (defined in [Section 12.2](#)) is noted the subject will discontinue treatments and will come off the study (please refer to [section 12.3](#) for Early Stopping Guidelines). Other subjects may continue to enroll.

If 2 DLTs are noted at the same NOTS (Number of Tumor Sites) level for a subject, study enrollment will be halted following Early Stopping Guidelines detailed in [Section 12.3](#).

Subjects as well as their family members will be educated about signs and symptoms of increased intracranial pressure and neurological deficit, for which the study investigators should be notified, and emergent medical attention should be sought.

This protocol will be uniform for all subjects enrolled in the trial.

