7.2 Trial Design

The trial will follow a 3+3 “NOTS” or Number of Tumor Sites escalation scheme. The “number of tumor sites” in reference to here in the number of openings in the blood brain barrier using Focused Ultrasound (FUS). Subjects will start the first cycle of the treatment arm with 1 tumor site and move on to incrementing NOTS levels as depicted in Figure 3, if no dose limiting toxicities

(DLTs) are observed (we use the term Dose Limiting Toxicity where dose = Number of Tumor Sites (NOTS)):

- 1 tumor site (level "NOTS Level A"),
- 2 tumor sites (level "NOTS Level B") or
- 3 tumor sites (level "NOTS Level C")

For a detailed description of DLTs please refer to [Section 12.2](#).

[figure not shown]

Figure 3: NOTS (Number of tumor Sites) Escalation Schema

For each subject the following FUS NOTS escalation scheme will be followed:

- Each subject will start off with receiving FUS treatment in 1 tumor site (NOTS Level A) for Cycles 1 and 2.
- If 0 DLTs are noted during pre-cycle 3 follow-ups and MRI (without contrast), the subject will receive FUS treatment at 2 tumor sites (NOTS Level B) in the 3rd cycle.
 - If 1 DLT is noted during pre-cycle 3 follow-ups and MRI (without contrast), the subject will discontinue treatments and will come off the study (please refer to [Section 12.3](#) for Early Stopping Guidelines). Other subjects may continue to enroll.
 - If 2 DLTs are noted at the same NOTS level, enrollment will be halted following Early Stopping Guidelines detailed in [Section 12.3](#).
- If 0 DLTs are noted during pre-cycle 4 MRI (without contrast) and follow-up, the subject will continue to receive FUS treatment at 2 tumor sites (NOTS Level B) in the 4th cycle.
 - If 1 DLT is noted during pre-cycle 4 follow-ups and MRI (without contrast), the subject will discontinue treatments and will come off the study (please refer to [Section 12.3](#) for Early Stopping Guidelines).

refer to [section 12.3](#) for Early Stopping Guidelines). Other subjects may continue to enroll.

- If 2 DLTs are noted at the same NOTS level, enrollment will be halted following Early Stopping Guidelines detailed in [Section 12.3](#).
- If 0 DLTs are noted during pre-cycle 5 MRI (without contrast) and follow-up, the subject will receive the next escalated FUS treatment at 3 tumor sites (NOTS Level C) in the 5th cycle.

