12.4 Early Withdrawal of Subjects

- If the subject fails to comply with the defined treatment plan and follow-up evaluations, the subject may be removed from the study at the discretion of the treatment investigator
- If the subject withdraws consent for continued participation, he/she will be removed from the study
- If the subject develops significant, new neurologic deficits or a change in level of consciousness a CT or MR scan may be performed to evaluate for hemorrhage/edema. If symptoms remain unmanageable by medications, craniotomy may be performed for resection of tumor, necrosis, or hemorrhage if medically indicated
- The reason for study removal and the date the subject was removed should be documented in the Case Report Form (CRF)
- If the treatment related toxicity experienced toxicity (Grade 2 or higher) persists for more than 21 days or ≥1 Dose Limiting Toxicity, the subject will not have the subsequent FUS and early withdrawal will be considered.

The primary endpoint of this study is safety. As such, subjects will be withdrawn from the study as per the guidelines outlined above. Should similar toxicities occur in more than one subject; early interruption of the study will be considered.

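### Section 12.1 gives conflicting retreatment instructions for an improving toxicity still at Grade 2, and Sections 7.2, 12.1 and 12.4 do not agree on what follows one DLT beyond withholding the next FUS

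*Combined protocol and SAP*

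**What the plan says.** **Persisting toxicity.** Three parts of Section 12.1 bear on whether the next FUS is given.

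- Halt sentence: "if grade 2 or higher toxicity is unresolved before the next scheduled FUS treatment, treatment will be halted". The same sentence makes re-evaluation wait for the toxicity's resolution, and it is not limited to treatment-related toxicity.
- Resume sentence, immediately after: "The treatment may be resumed for the subject if the toxicity is resolving before the subsequent scheduled FUS treatment". It names no grade.
- Criteria to proceed, further down: "Resolving treatment related toxicity experienced in prior FUS /treatment to grade 2 or less". This is limited to treatment-related toxicity. The same short list also contains "Patient decides to withdraw".

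**One DLT.** Four places state a consequence.

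- Section 7.2, at each pre-cycle checkpoint and again for events within a cycle: "the subject will discontinue treatments and will come off the study".
- Section 12.1, paragraph after the proceed list: the same instruction as 7.2 for a DLT within a cycle.
- Section 12.1, earlier sentence on Grade 2 or higher treatment-related toxicity: if it "persists for more than 21 days or there is ≥ 1 Dose Limiting Toxicity (DLT), the subject will not have the subsequent FUS". Study participation is not mentioned.
- Section 12.4, same two triggers: "the subject will not have the subsequent FUS and early withdrawal will be considered".

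Section 12.4 also states that safety is the primary endpoint, and Section 12.1 closes by saying that the protocol applies uniformly to all subjects.

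**The concern.** Escalation in Section 7.2 is within subject: one site in Cycles 1 and 2, two in Cycles 3 and 4, three in Cycles 5 and 6. Each decision to give or withhold a session therefore affects how much exposure a subject has at a level, whether the subject reaches Levels B and C, and which toxicities can be seen there. If the text supports two different actions for the same child, the safety summary depends partly on which sentence was followed. Nobody could later say whether giving the session was a protocol deviation.

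The DLT wording raises a related issue. Whether a subject with a DLT may have later treatment or remain on study decides what data that subject contributes afterwards.

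**Working it through.** No figure in the plan is in dispute, so the check is to apply each instruction to the same case.

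**Case 1: toxicity present before the next FUS.**

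| State before the next FUS | Halt sentence | Resume sentence | Proceed criterion |
|---|---|---|---|
| Treatment-related, Grade 2, static or worsening | Halt | Not met (not resolving) | Not met (not resolving) |
| Treatment-related, Grade 2, improving | Halt until resolution | May resume | Met |
| Not treatment-related, Grade 2, improving | Halt until resolution | May resume | Does not address it |

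The second row is the contradiction. It turns on three mismatches:

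1. State: *resolution* in the halt sentence, *resolving* in the other two.
2. Grade: Grade 2 is enough to halt, yet is accepted by the proceed criterion; the resume sentence gives no grade.
3. Scope: any toxicity in the halt sentence, only treatment-related toxicity in the proceed criterion.

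The 21-day clause does not settle the second row, because it acts only once the toxicity has lasted more than 21 days.

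The case can arise. Section 12.2 gives Grade 3 thrombocytopenia without bleeding, Grade 3 or 4 lymphopenia and Grade 3 neutropenia without fever as examples of exceptions to the DLT definition. A subject with such an event who has improved to Grade 2 falls under the retreatment text of 12.1. Section 3.1.4 lists these cytopenias among panobinostat's most common haematologic abnormalities (incidence at least 60%, grade not stated). That shows the case is realistic, not how often it will occur.

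**Case 2: one DLT.**

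| Place | Next FUS | Later treatment | Study participation |
|---|---|---|---|
| 7.2 | Withheld | Ended | Ended |
| 12.1, later paragraph | Withheld | Ended | Ended |
| 12.1, earlier sentence | Withheld | Not stated | Not stated |
| 12.4 | Withheld | Not stated | Withdrawal considered |

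The first column is unanimous; the other two are not. Sections 7.2 and 12.1 also provide for two DLTs at one level in a single subject. That is hard to reach if one DLT removes the subject, unless both arise together, so it adds to the doubt about what one DLT triggers.

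**Bounds on size.**

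- Sessions per subject: Section 7.5 defines a cycle as 2 weeks of 3 treatment days, with 6 cycles, so 6 × 2 × 3 = 36. The first session follows no earlier FUS, leaving at most 36 − 1 = 35 at which toxicity from a previous session could be assessed. If Days 1, 3 and 5 are read as the only treatment days in a cycle, the figures are 6 × 3 = 18 and 18 − 1 = 17. These count decision points, not conflicts.
- Weight of one subject: Section 10.1 gives 3 to 15 subjects. One is 1/15 = 6.7% at the maximum and 1/3 = 33.3% at the minimum.

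**The case against.** The best defence is that the Grade 2 text can be read in sequence: hold at the next session, re-evaluate, then resume at the following one if the toxicity is improving. This partly stands. It disposes of static and worsening Grade 2 events, which meet only the halt sentence. A reader might infer that every session preceded by a persisting Grade 2 event is both barred and allowed; the documents do not support that, because both permissive passages require the toxicity to be resolving. The sequential reading fails for the improving case, since the halt sentence ties re-evaluation to resolution while the proceed criterion accepts residual Grade 2.

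On DLTs, a reader who stops at the earlier sentence of 12.1 might conclude that 12.1 bars only the next FUS. It does not: its later paragraph repeats the mandatory rule of 7.2, and ending treatments there would naturally include panobinostat. The earlier sentence is compatible with that rule but incomplete. One can add that 12.4 goes on to say subjects will be withdrawn under the guidelines above it. That does not remove the tension, because the guideline above it for a DLT is the one that only considers withdrawal.

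Recruitment is at one centre and 12.1 gives the judgement on proceeding to the principal investigator, so variation between investigators is a weak argument. That is fair. But that judgement is conditioned on recovery from the event, the other stated discretion concerns timing of doses, and consistency across subjects and classification of deviations still need one rule.

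The withdrawal item in the proceed list is an evident slip and would mislead nobody in practice. It needs correcting but adds little weight.

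**Conclusion.** The plan is wrong as written on two limited points. First, for a treatment-related toxicity that is improving but still Grade 2 before the next FUS, Section 12.1 gives incompatible instructions, with scopes that also differ. Second, after one DLT the passages agree that the next FUS is withheld but not on whether later treatment and study participation must end. The mandatory rule of 7.2 and the later paragraph of 12.1 sits beside a discretionary bullet in 12.4 and an incomplete sentence in 12.1.

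Both are contradictions of text and depend on no numerical assumption. Their practical effect cannot be sized from the documents, which give no rate or duration of Grade 2 toxicity on this regimen. In particular, the short interval between sessions might suggest that Grade 2 events will usually persist to the next one; nothing in the documents supports that. What can be said is that with at most 15 subjects and safety as the primary endpoint, a single decision that could properly have gone either way affects a visible share of the evidence. That justifies correction before the text is relied on.

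**What to change.** Amend the wording as follows, leaving the choice of clinical rule to the sponsor.

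1. In 12.1, reconcile the halt sentence, the resume sentence and the proceed list so that one grade threshold, one state (resolved or resolving) and one scope (any or treatment-related toxicity) apply throughout.
2. Remove the patient-withdrawal item from the criteria to proceed.
3. Make Section 7.2, both statements in 12.1 and the 12.4 bullet give the same consequence of one DLT for later FUS, panobinostat and study participation. In the same pass, check that the provision for two DLTs in one subject is still reachable.

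The cost is a protocol wording amendment. Sample size, endpoints and analyses are unchanged.

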12.2 Dose Limiting Toxicities

Dose limiting toxicities (DLT) will be defined as any new (or increased from baseline), treatment related (drug and/or device):

1. Neurological deficits based on neurological examination which are grade 3 or greater nervous system adverse events at least possibly attributed to sonication (as defined by CTCAE v5.0).

2. Grade 2 or higher symptomatic intracranial hemorrhage or stroke.

These deficits include but are not limited to changes in level of consciousness, new onset speech difficulties (aphasia, mutism, dysarthria), confusion, visual field deficits, focal weakness, seizures. The DLT period is defined as starting the day of the first scheduled FUS treatment and lasting until 14 days after the last scheduled FUS treatment.

Furthermore, DLT criteria include any systemic treatment- related Grade 3 or higher hematologic or non-hematologic toxicity within a period of 14 days after the scheduled FUS treatment. Examples of exceptions could include:

- I. Grade 3 thrombocytopenia without bleeding, Grade 3 or 4 lymphopenia, Grade 3 neutropenia without fever.
- II. Nausea, vomiting or diarrhea responding to medical management within 48 hours
- III. Electrolyte disturbances that are asymptomatic and response to supportive care within 48 hours; hyperglycemia \leq 12 hours

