During the mid-cycle at different time-points (as described in section [7.4](#) and [7.5](#) below), MRIs with gadolinium contrast will be conducted to ensure proper opening and closure of the BBB. If the subject's MRI shows any anomaly, the subject will be removed from the study and will continue on regular drug treatment as decided by the study team. The subject will follow the schema below.

7.4 Schematic Overview of Panobinostat Treatment for Week 1** Cycle 1

**Week 2 of each cycle will follow a similar schema with the exception of MRIs with contrast conducted to evaluate opening and closing of the BBB.

**Cycles 2 and 4 will follow a similar schema with the exception of an MRI to confirm closure of the BBB on Day 3.

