7.5 Treatment MRIs

Treatment MRI breakdown:

- 1 cycle of Panobinostat= 2 weeks of 3 alternate treatment days. Subjects will undergo 6 cycles, each spaced 1 week apart.
- In each cycle, subjects will receive Focused Ultrasound (NgFUS) and injection of DEFINITY® microbubbles using NgFUS system in the Radiation Oncology Suite on Days 1, 3, and 5 (all treatment days).
- **MRI to Determine Opening of Blood Brain Barrier:** On Week 1 Day 1 of each cycle, 2-4 hours post FUS treatment with DEFINITY® microbubbles on Day 1, subjects will receive an MRI with injection of Gadolinium contrast.
- Treatment includes receiving Oral Panobinostat at 15 mg/m² on the days of NgFUS treatment.
- **MRI to Confirm Closure of Blood Brain Barrier:** On Week 1 Day 3 of every other cycle (Cycles 1, 3 and 5), subjects will undergo MRI with gadolinium pre Day 3 FUS treatment to ensure closure of the blood brain barrier. This MRI will be conducted within 24-48 hours of the completion of the Day 1 FUS treatment.
- A number of tumor sites (NOTS) escalation scheme for the number of tumor sites targeted by FUS will be followed as laid out in [section 7.2](#). As stated in the section, an MRI (without contrast) will be performed prior to each escalation to clear the subject of any possible DLTs and increase in tumor size.

Subjects will receive FUS treatment in the Radiation Oncology Suite and drug treatments in either the Outpatient Clinic on HIP-7 or in Radiation Oncology immediately after the FUS treatment. Subjects will be monitored by the study team with Neurological Exams on treatment days, as determined necessary. Subjects will not be kept as inpatients for treatment days and will be discharged following completion of treatment day, unless deemed necessary by the study team.

See [Appendix A](#) and [B](#) on pages 47 and 49 respectively for a detailed breakdown of visits and data collected.

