Appendix B- Study Calendar

- 1 cycle of Panobinostat= 2 weeks of 3 alternate treatment days. Subjects will undergo 6 cycles, each spaced 1 week apart.
- In each cycle, subjects will receive Focused Ultrasound (NgFUS) and injection of DEFINITY® microbubbles and using NgFUS system in the Radiation Oncology Suite on Days 1, 3, and 5 (all treatment days).

| | Screening | Treatment Phase | | | | Follow-up |
|--------------------------------------------------|------------------|------------------------|---------------------|----------------|----------------|------------------|
| Time points | -7 days | Day 1 | +12-+48hours | Day +3 | Day +5 | +90 days |
| Height | X | | | | | X |
| Weight | X | | | | | X |
| Medical History | X | | | | | |
| Demographics | X | | | | | |
| Vital signs | X | | | | | X |
| Informed Consent | X | | | | | |
| CBC w/diff, plts | X | | X ^c | | | X |
| Serum chemistry (BMP and hepatic function panel) | X | | X ^d | | | X |
| Coagulation Panel (PT, INR, PTT) | X | | X ^e | | | |
| Concomitant Medication Review | X | | | | | X |
| EKG | X | | X ^f | | | |
| Focused Ultrasound Treatment | | X ^b | | X ^b | X ^b | |
| Performance Status | X | X | | | | X |
| MRI | X ^a | | X ^g | X ⁱ | | X ^j |
| Oral Panobinostat | | X ^h | | X ^h | X ^h | |
| Physical Exam | | | X ^k | | | |

a- MRI with gadolinium contrast to be performed for screening purposes.

b- In each cycle, subjects will receive Focused Ultrasound (NgFUS) and injection of Microbubbles using NgFUS system in the Radiation Oncology Suite on Days 1, 3, and 5 (all treatment days).

c- Perform one approximately 12-24 hours post NgFUS

d- Perform once approximately 12-24 hours post NgFUS

e- Perform once approximately 12-24 hours post NgFUS.

f- An electrocardiogram (EKG) will be performed once approximately 12—48 hours post NgFUS.

g- **MRI to Determine Opening of Blood Brain Barrier:** During Week 1 Day 1 of each cycle, 2-4 hours post FUS treatment with Microbubbles on Day 1, subjects will receive an MRI with injection of Gadolinium contrast.

h- Treatment includes receiving Oral Panobinostat at 15 mg/m².

i- **MRI to Confirm Closure of Blood Brain Barrier:** On Week 1 Day 3 of every other cycle (Cycles 1, 3 and 5), 24-48 hours post Day 1 FUS treatment with Microbubbles, subjects will undergo MRI with gadolinium pre Day 3 FUS treatment to ensure closure of the blood brain barrier.

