j Follow-up MRIs will be conducted every 8 weeks as per SOC as discussed by the study team

k- The subject will be monitored with standard Physical Exam during each cycle and between every cycle.

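### No blood test is scheduled at the 0-DLT gates before Cycles 3 and 5 or late in the last 14-day window, although laboratory toxicities count as DLTs

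*Combined protocol and SAP*

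**What the plan says.** Section 12.2 defines neurological DLTs and adds systemic hematologic and non-hematologic toxicity of Grade 3 or higher arising "within a period of 14 days after the scheduled FUS treatment". The listed exceptions are examples. For blood counts they cover uncomplicated Grade 3 thrombocytopenia and neutropenia, and lymphopenia of Grade 3 or 4. Brief asymptomatic electrolyte changes and short hyperglycemia are also excepted.

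Section 7.2 escalates a subject from one site to two before Cycle 3, and from two to three before Cycle 5, if no DLT is seen at pre-cycle follow-up and on a non-contrast MRI. It does not say what the follow-up consists of. Section 7.5 says that "an MRI (without contrast) will be performed prior to each escalation to clear the subject of any possible DLTs and increase in tumor size", and refers the reader to Appendices A and B "respectively for a detailed breakdown of visits and data collected".

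Appendix B marks CBC and chemistry in three columns: screening, +12 to +48 hours, and the +90-day follow-up. Note c (CBC) reads "Perform one approximately 12-24 hours post NgFUS" and note d (chemistry) reads "Perform once approximately 12-24 hours post NgFUS". Neither says whether this means after every FUS or once per cycle. For the time between cycles, note k states: "The subject will be monitored with standard Physical Exam during each cycle and between every cycle".

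On timing, section 7.5 states: "Subjects will undergo 6 cycles, each spaced 1 week apart". Section 7.4 adds that "Week 2 of each cycle will follow a similar schema", apart from the contrast MRIs.

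**The concern.** The DLT definition and the assessment schedule do not match. A Grade 4 platelet or neutrophil count, Grade 3 anemia, or a Grade 3 liver or creatinine change is a DLT if treatment-related. Neither an MRI nor, reliably, a physical exam will show it.

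Two things are at stake. The first is the child. Panobinostat is not dose-reduced (12.1), thrombocytopenia is among its laboratory abnormalities with an incidence of at least 60% (3.1.4), and hemorrhage is a named FUS risk (5.4). The platelet floor of 100,000/µL is an entry criterion (8.1.2), and 12.1 sets no count for re-treatment. A subject could pass the gate, be sonicated at more sites and be redosed without a current platelet count.

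The second is the primary result. Section 6.1 assesses safety partly by laboratory studies. If the last part of the final 14-day window has no scheduled draw, laboratory DLTs at three sites, the highest level, can be undercounted.

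**Working it through.** The plan gives no figure for laboratory age or coverage, so there is nothing to reproduce first. The check is day-counting.

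**Inputs.** A cycle is two treatment weeks plus one week off, so 21 days (7.5). FUS falls on Days 1, 3, 5, 8, 10 and 12 (7.5, with Week 2 like Week 1 from 7.4). Level A is Cycles 1–2, B is 3–4 and C is 5–6 (7.2). The window is 14 days (12.2). A draw follows FUS by up to 24 hours (notes c and d), taken as one day. Assumption: the gate is on Day 1 of the new cycle.

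**Dates.** Study day = 21 × (cycle − 1) + day.
- Last Level A FUS: 21 + 12 = 33. Gate to B: 42 + 1 = 43.
- Last Level B FUS: 63 + 12 = 75. Gate to C: 84 + 1 = 85.
- Last Level C FUS: 105 + 12 = 117. Window closes: 117 + 14 = 131. The +90-day column, read as one visit: 117 + 90 = 207.

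**Age of the last scheduled result at the gate.**

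| Reading | Gate to B | Gate to C |
|---|---|---|
| Draw after every FUS | 43 − 34 = 9 days | 85 − 76 = 9 days |
| One draw per cycle, after Day 1 | 43 − 23 = 20 days | 85 − 65 = 20 days |

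A 12-hour draw adds half a day. If FUS were given in Week 1 only, the ages would be 16 and 20 days. If cycles were 30 days apart, to fill the 6 months in the synopsis, the every-FUS age would be 61 − 43 = 18 days.

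**What happens just after the gate.** The last Level A window runs to 33 + 14 = 47. Under both readings in the table the next draw is Day 44, inside that window but after the first escalated session. A persisting abnormality is found then; one that recovers sooner is not.

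**End of Level C.** The last scheduled draw is Day 118 (every FUS) or Day 107 (once per cycle). No draw is fixed between then and Day 131.

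**Share of Level C laboratory DLTs starting after the last scheduled draw.** Assume onset uniform over the 14 days, equal risk for each of the 12 sessions, and detection by blood test only. Count the days of each session's window that lie after the last draw and divide by 12 × 14 = 168.
- Every FUS (draw on Day 118): sessions on Days 106, 108, 110, 113, 115 and 117 give 2 + 4 + 6 + 9 + 11 + 13 = 45; 45/168 = 26.8%.
- Once per cycle (draw on Day 107): Days 94 and 96 give 1 + 3, Day 106 gives 13, and the five later sessions give 5 × 14 = 70; total 87; 87/168 = 51.8%.

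If every onset falls in the first week of the window the shares are 14.3% and 48.8%; if in the second week, 39.3% and 54.8%. Earlier abnormalities are assumed to last until the next draw within the treatment course, which favors the plan.

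**The case against.** The strongest reply is that Appendix B is not a complete list. It omits the non-contrast checkpoint MRI that 7.2 and 7.5 require, has no pre-cycle column, and does not mark a physical exam at screening although Appendix A lists one. Section 7.2 gates on follow-up as well as MRI, and that follow-up might include blood tests. The schematics, including the one in 7.4 and Figure 3, are not in the text available here. Section 11.1 also requires all CTCAE events to be captured for 30 days after treatment, which covers the window. All of this stands as uncertainty. None of it fixes a draw at a gate or late in the last window.

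A reader might infer more than the documents support:

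- *That no blood is drawn in the last window.* This holds for the last FUS only on the once-per-cycle reading. On the every-FUS reading there is a 12–24-hour draw first, and none of the 36 sessions lacks a draw in its window; on the once-per-cycle reading 20 of 36 do.
- *That laboratory DLTs missed at the gates are lost.* Most would be late findings, made on Day 2 of the new cycle. Loss is mainly a Level C matter.
- *That the halt for unresolved Grade 2 toxicity in 12.1 cannot work.* On the every-FUS reading, draws on Days 2, 4, 6, 9 and 11 precede each later FUS within the cycle.
- *That the next test is certainly Day 207.* The same column holds MRIs that note j places every 8 weeks, so it may mark a period. Even so, no draw by Day 131 is assured.
- *That the stopping rule loses a known amount of sensitivity.* With 6 subjects all reaching Level C, a 20% DLT risk and half of DLTs detectable only by blood test, the chance of DLTs in two or more subjects falls from 0.345 to 0.279 or 0.219. Those inputs are assumed, and treatment ends at progression (9.1), so this is an illustration only.

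**Conclusion.** The mismatch is real and cheap to correct. As written, the schedule allows escalation and redosing on a blood result about 9 or 20 days old, depending on how notes c and d are read, and fixes no draw in the later part of the final window. The 27% and 52% apply to Level C DLTs that only a blood test can detect, and rest on uniform onset and equal risk per session; the share of all DLTs that are of this kind is unknown. The ages rest on the gate falling on Day 1; an earlier pre-cycle visit would shorten them.

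The documents support saying that laboratory DLTs at three sites *can* go uncounted, not that the count *will* be too low. Unscheduled tests or the undefined follow-ups may close part of the gap.

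**What to change.** - **Appendix B and 7.2:** schedule CBC with differential and serum chemistry on the day of, or the day before, Day 1 FUS of Cycles 3 and 5, and preferably of Cycles 2 to 6. Results are reviewed before the 0-DLT decision and before FUS. Repeat both about 7 and 14 days after the subject's last FUS, whenever that is; at minimum once near Day 14.
- **Notes c to e:** state whether the draw is after every FUS or once per cycle.
- **7.5:** base clearance for escalation on examination, blood results and MRI together.

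Results at the gate would then be 0–1 day old. If the abnormality persists, a gate-day draw would find 39/45 = 87% (every FUS) or 81/87 = 93% (once per cycle) of the laboratory DLTs that start after the last draw now scheduled before the gate. A draw the day before would find 36/45 = 80% or 78/87 = 90%.

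**Cost:** up to seven extra draws per subject (five before Cycles 2–6, two after the last FUS), so at most 7 × 15 = 105. The five pre-cycle draws can be taken at Day 1 visits already planned; the one or two after the last FUS need a visit not now scheduled. A same-day draw needs same-day results. More laboratory DLTs will be found, so some children will stop or pause earlier.
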